2.2. Endpoints

2.2.1 Primary Efficacy Endpoints:

CLUE Overall Comfort

Overall comfort scores will be assessed using the Contact Lens User Experience (CLUETM)⁷ questionnaire at the two-week follow-up. CLUE is a validated patient-reported outcomes questionnaire to assess patient-experience attributes of soft, disposable contact lenses (comfort, vision, handling, and packaging) in a contact-lens wearing population in the US, ages 18-65. Derived CLUETM scores using Item Response Theory (IRT) follow a normal distribution with a population average score of 60 (SD 20), where higher scores indicate a more favorable/positive response with a range of 0-120. A 5-point increase in an average CLUETM score translates into 10% shift in the distribution of scores for population of soft contact lens wearers.⁷ The handling scores will be generated using the flexMIRT software Version 3 or higher (Chapel Hill, NC).

Distance Monocular Contact Lens Visual Acuity

Distance monocular contact lens visual performance (logMAR) is assessed for each subject eye at the two-week follow-up evaluation using EDTRS charts using high illumination and high contrast charts.

Vision Satisfaction in Bright Lighting

Vision satisfaction in bright lighting will be assessed using the individual item (Item ID: V015_1) "I was satisfied with the quality of my vision in bright lighting" from the CLUETM questionnaire. This item uses the response scale, 1: Strongly Disagree, 2: Disagree, 3: Neither Agree nor Disagree, 4: Agree and 5: Strongly Agree.

2.2.1. Primary Safety Endpoints:

Slit Lamp Findings (Grade 3 or Higher)

Slit Lamp Findings will be assessed for each subject eye at all study visits (schedule and unscheduled). The percentage of eyes with Grade 3 or higher slit lamp findings will be analyzed and will include corneal infiltrates.

Fit Acceptance Rate

Acceptable lens fit will be assessed at all study visits (scheduled and unscheduled) for each subject eye. Fit acceptance rate will be based on the lens fit acceptance of eyes wearing the Test lens only. Fit rates of the Control lens will also be collected but are not a primary endpoint.

2.2.2. Secondary Endpoints:

CLUE Overall Vision and Handling

Overall vision and handling scores will be assessed using the Contact Lens User Experience (CLUE)⁷ questionnaire at the two-week follow-up.

2.2.3. Other Endpoints:

Average daily wear time (in Hours):

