5.2. Masking

The dynamic nature of the Test lens makes it impossible to completely mask the study lens assignment. The subjects will be aware if they are wearing a photochromic lens or non-photochromic lens due to the function nature of the photochromic dye. Additionally, there is a slight difference in physical appearance between the Test and Control lenses when the Test lens is activated by outdoor light that makes it difficult to mask investigative personnel. However, the Control lens will be masked in the event that OASYS is the subject's habitual lens by chance, making this a partial-subject masked study.

Every attempt will be made to keep the other clinical trial personnel involved in the study (e.g. Data management, Biostatistician and Clinical Operations) unaware of the lens assignment. The identity of the study lenses will be masked by over labeling the blister packs with a label containing the study number, lot number, sphere power, expiration date and the randomization codes. Only the personnel involved in the over labeling and the Statistician generating the randomization scheme will have access to the decode information translating the randomization codes into Test and Control arms. The medical monitor will also have access to the decode information in case breaking the mask is necessary for the urgent medical treatment of a subject.

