7.2. Detailed Study Procedures

VISIT 1

The subjects must present to Visit 1 wearing their habitual contact lenses.

	Visit 1: Screening			
Step	Procedure	Details		
1.1	Statement of Informed Consent	Each subject must read, understand, and sign the Statement of Informed Consent before being enrolled into the study. The Principal Investigator or his/her designee conducting the informed consent discussion must also sign the consent form.		
r.		Note : The subject must be provided a signed copy of this document.		
1.2	Demographics	Record the subject's date of birth, gender, race and ethnicity.		
1.3	Medical History and Concomitant Medications	Questions regarding the subjects' medical history and concomitant medications.		
1.4	Habitual Lenses	Questions regarding the subject's habitual lens type and parameters.		
1.5	Eligibility after Screening	All responses to Screening Inclusion Criteria questions must be answered "yes" and all responses to Exclusion Criteria must be answered "no" for the subject to be considered eligible.		

	Visit 1: Screening			
Step	Step Procedure Details			
		If the subject is deemed to be ineligible after screening, proceed to Final Evaluation and complete Subject Disposition. Refraction and Biomicroscopy forms are not required.		

	Visit 1: Baseline			
Step	Procedure	Details		
1.6	Baseline Questionnaire	The subject will respond to the CLUE Baseline Questionnaire.		
1.7	Entrance Visual Acuity	Record the distance Snellen visual acuity (OD, OS, and OU) to the nearest letter with their habitual contact lens correction in place. Subjects must read the smallest line until at least 50% of the letters are read incorrectly.		
1.8	Remove Habitual Lens	The subject's habitual lenses will be removed and stored in their own lens case. If they forgot to bring their lens case, one will be provided to them.		
1.9	Iris Color	The investigator will record the subject's iris color based on the scale provided.		
1.10	Keratometry	Record the keratometry readings OD and OS in diopters. This can come from any appropriate instrument so long as the same instrument is used at the Final Evaluation.		
1.11	Subjective Sphero- cylindrical Refraction	Complete subjective spherocylindrical refraction and record the resultant distance visual acuity (OD, OS, and OU) to the nearest letter. Best corrected distance visual acuity (BVA) must be 20/25+3 or better in each eye.		

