2.1.	Adverse Events and Concomitant Medications Review	Review any changes to the subject's medical history or concomitant medications from the previous study visit. Record any changes, and any adverse events.		
2.2.	Wearing Time	Record the average wearing time and comfortable wearing time.		
2.3.	Compliance	Confirm compliance with the prescribed wear schedule.		
2.4.	Subject Reported Ocular Symptoms	Subjects will respond to a verbal open-ended symptoms questionnaire.		
2.5.	Follow-Up Questionnaires	The subject will respond to the Follow-Up Questionnaires.	1.5 2.5	
2.6.	Visual Acuity	Record the distance Snellen visual acuity with the contact lenses (OD, OS, and OU) to the nearest letter. Subjects must read the smallest line until at least 50% of the letters are read incorrectly.		
2.7.	Distance ETDRS LogMAR Visual Acuity	Perform 4 m distance ETDRS LogMAR visual acuity test OD and OS under the following conditions: Bright room illumination / high contrast charts a. Room illumination > 400 lux b. Chart luminance 120-200 cd/m ² c. One high contrast chart per eye. 1) OD: chart HC-1 2) OS: chart HC-2		
2.8.	Subjective Lens Fit Assessment	 Evaluate overall lens fit acceptance (acceptable or unacceptable) based on centration, movement and other fitting characteristics. An unacceptable fit is deemed by one of the following criteria: limbal exposure at primary gaze or with extreme eye movement edge lift 		

	Visit 2: Treatment 1 Follow-Up 1			
Step	Procedure	Details		
		 insufficient or excessive movement in all three of the following conditions: primary gaze, up gaze, and Josephson push up 		
2.9.	Lens Wettability	Perform the white light lens wettability procedure and record the results.		
2.10.	Surface Deposits	Record any front and back surface lens deposits.		
2.11.	Lens Removal & Storage	Both lenses will be removed and stored wet in a labeled container with Opti-Free PureMoist. The lenses can be stored refrigerated or frozen prior to shipment back to the Sponsor. Lenses will be stored at JJVCI for 45 days after LSLV for laboratory testing (Section 7.4).		

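### At Visit 2 the questionnaire behind two primary endpoints follows a spoken review of problems, comfort and symptoms by staff who are hard to mask; putting it first would be a cheap improvement

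*Protocol*

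**What the plan says.** Protocol 7.2 numbers the Visit 2 steps. Step 2.1 reviews history and medications: "Record any changes, and any adverse events". Step 2.2 reads "Record the average wearing time and comfortable wearing time", step 2.3 "Confirm compliance with the prescribed wear schedule", and step 2.4 "Subjects will respond to a verbal open-ended symptoms questionnaire". Only then comes step 2.5: "The subject will respond to the Follow-Up Questionnaires". Acuity, lens fit, wettability, deposits, lens removal and slit lamp follow as steps 2.6 to 2.12.

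Step 2.5 does not name CLUE. The link is in Protocol 2.2, which takes the first primary endpoint from that instrument at two weeks ("Overall comfort scores will be assessed using the Contact Lens User Experience"). It takes the bright-light item from the same questionnaire, and both secondary endpoints (vision and handling) as well. Protocol 2.3.1 requires every primary hypothesis to be met, so either patient-reported endpoint can decide the study.

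On masking, Protocol 5.2 (repeated in SAP 2.4) says that subjects will know whether they wear a photochromic lens. It adds that the activated Test lens differs in appearance in a way "that makes it difficult to mask investigative personnel".

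**The concern.** Subjects are questioned aloud about problems, comfortable wear, compliance and symptoms just before they rate comfort. The questioner may know or guess the lens, and the subject does know whether it is photochromic. If staff probe harder or more lightly for one lens, or if the same questions work differently on subjects who know what they are wearing, the interview could carry into the ratings. In a non-inferiority comparison such a shift moves the estimate directly toward or away from the margin. Neither the planned models nor the ITT repeat could separate it from a real lens effect.

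Comfort is the more exposed endpoint. Step 2.2 raises comfort itself, and step 2.4 invites complaints immediately beforehand. No step from 2.1 to 2.4 asks specifically about vision in bright light.

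**Working it through.** The point is about order and masking, and the plan states no figure for it. The check is therefore mainly a reading of the steps.

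| Visit 2 step | Content | Relation to the ratings |
|---|---|---|
| 2.1 | Medications and adverse events | Before; raises problems |
| 2.2 | Average and comfortable wear | Before; raises comfort |
| 2.3 | Compliance | Before |
| 2.4 | Spoken symptoms questions | Immediately before; raises problems |
| 2.5 | Questionnaires | The ratings themselves |
| 2.6 to 2.12 | Acuity, fit, lens surface, lens removal, slit lamp | After |

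**What a bias needs.** Write the expected observed mean difference as δ + (b_T − b_C), where δ is the true Test-minus-Control difference and b_T and b_C are the average priming shifts in each arm. If b_T = b_C the second term is zero. Only a difference between the arms matters, and the documents give no value or sign for it.

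**Scale for comfort, under assumed shifts.** Inputs: SD 21 and planned difference 2 points (Protocol 14.2), margin −5 (Protocol 2.3.1), 112 completers per arm (Protocol 14.2), and a two-sided 95% interval, i.e. one-sided 2.5% (Protocol 14.5). A two-sample t test stands in for the Bayesian model, without covariate adjustment.

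- Standard error = 21 × √(2/112) = 2.806; 222 degrees of freedom; critical value 1.971.
- If the true difference is −5, the noncentrality is shift/2.806.
- At the planned +2, it is (7 + shift)/2.806.

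| Assumed differential shift (points) | True difference −5: chance of declaring non-inferiority | Planned +2: power |
|---|---|---|
| 0 | 2.5% | 70% |
| +1 / +2 / +3 (toward Test) | 5.4% / 10.6% / 18.5% | 81% / 89% / 94% |
| −1 / −2 / −3 (against Test) | 1.0% / 0.4% / 0.1% | 57% / 43% / 29% |

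The 70% starting point is below the 87% in Protocol Table 12. The stated inputs give 70% at one-sided 2.5% and 80% at one-sided 5%. About 87% results from the unrounded historical difference, 66.66 − 63.90 = 2.76, at one-sided 5%. That is a separate matter and does not affect this point.

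**Scale for bright light.** The historical Control rate is (51 + 130)/242 = 74.8% (Protocol Table 11) and the margin is 10 percentage points. With 112 per arm, a normal approximation and unpooled variance, an assumed shift of +2 or +5 percentage points toward Test at the margin raises the false-positive chance from 2.5% to 5.2% or 13.1%.

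**The case against.** The strongest reply is that steps 2.1 to 2.4 are the same in both randomised arms, that an open-ended question is about the least leading kind, and that nothing shows staff question differently by lens. This stands as a limit: the plan leaves a route open, but no bias is demonstrated.

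Staff unmasking is also narrower than it may sound. Protocol 5.2 ties the visible difference to a lens activated by outdoor light, Protocol 1 says the lens lightens when that light is absent, blister packs are over-labelled, and steps 2.1 to 2.4 precede any eye examination at that visit. Staff may still learn the lens from the subject's own answers, but the documents do not show that interviewers generally know it.

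The administration instructions cannot be seen. Appendix A survives only as page headers, and the SAP refers the symptoms procedure to a protocol Appendix D that is not in the text supplied. Self-completion or other safeguards cannot be ruled out. Nor does the protocol say that the numbered order is mandatory. All of this lowers confidence but does not make the present order preferable.

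A reader might also infer that the baseline adjustment is compromised, because at Visit 1 step 1.6 ("The subject will respond to the CLUE Baseline Questionnaire") comes well before the symptoms question at step 1.20. The documents do not support this. Baseline CLUE is collected before randomisation, in the same way for both arms, and enters as a regression covariate rather than through a change score (Protocol 14.5, SAP 10.1). It need not be taken under the same conditions as the outcome. The questionnaire precedes the eye examinations at both visits, staff questions come before it at Visit 1 too (steps 1.3 and 1.4), and the bright-light model has no baseline term.

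**Conclusion.** The point holds as a cheap improvement, not as an error in the plan. Two primary and both secondary endpoints are rated directly after a spoken review of problems and comfort by staff who are hard to mask, and no visible text shields the ratings from that review. If the questioning or its effect differs by lens, the ratings could shift, mainly for comfort.

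The size is unknown. The figures above show how sensitive the decision is to shifts that are assumed, with no basis in the documents for any value. Expressing such a shift as a share of the 5-point margin would not add evidence. The direction is equally open: the result could be false success or needless failure.

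A reader might infer that reordering would make these endpoints free of masking bias. It would not. Subjects' own knowledge of the lens acts on self-report in any order and is probably the larger source. The reorder closes only the avoidable part, the staff interview.

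**What to change.** In Protocol 7.2, make the Follow-Up Questionnaires the first step of Visit 2, before the present steps 2.1 to 2.4. Keep the other steps in their present order and match the Visit 2 eCRF sequence. No procedure, staff, visit time or analysis is added. The small downside is that the order may then differ from that in the historical studies behind the planning values; the randomised comparison is not affected, because both arms follow the same order.

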2.3. Hypotheses

2.3.1. Primary Hypotheses

All the following primary hypotheses must be met for the objectives of this study to be satisfied:

1. Subjects wearing the JJVCI Investigational contact lenses on a daily wear basis will have patient reported comfort at the 2-Week Follow Up visit that is non-inferior to that of

subjects wearing predicate device on a daily wear basis. A non-inferiority margin of -5 CLUE points will be used.

- 2. Subjects wearing the JJVCI Investigational contact lenses on a daily wear basis will report distance monocular visual acuity (logMAR: bright room luminance/high contrast charts) at the 2-Week Follow Up visit that is non-inferior to that of subjects wearing predicate device on a daily wear basis. A non-inferiority margin of 0.05 logMAR will be used.
- 3. Subjects wearing the JJVCI Investigational contact lenses on a daily wear basis will have patient reported outcome (Agree and Strongly Agree) on the Quality of Vision in Bright Light at the 2-Week Follow Up visit that is non-inferior to that of subjects wearing predicate device on a daily wear basis. A non-inferiority margin of 10% will be used.
- 4. Subjects wearing the JJVCI Investigational contact lenses on a daily wear basis will have a percentage of any Grade 3 or higher slit lamp findings at all visits (scheduled and unscheduled) that is non-inferior to that of subjects wearing predicate device on a daily wear basis. A non-inferiority margin of 5% will be used.
- 5. At least 90% of eyes wearing the JJVCI Investigational contact lenses on a daily wear basis will have acceptable fits across the fitting and follow-up visits.

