1.21	Visual Acuity	Record the distance Snellen visual acuity with the contact lenses (OD, OS, and OU) to the nearest letter. Smaller lines must be shown until the subject incorrectly identifies at least 50% of the letters.		
1.22	Subjective Lens Fit Assessment	 Evaluate overall lens fit acceptance (acceptable or unacceptable) based on centration, movement and other fitting characteristics. An unacceptable fit is deemed by one of the following criteria: limbal exposure at primary gaze or with extreme eye movement edge lift excessive movement in primary and up gaze insufficient movement in all three of the following conditions: primary gaze, up gaze, and Josephson push up Note: if lens fit is unacceptable subject will be discontinued from the study. 		
1.23	Lens Wettability	Perform the white light lens wettability procedure and record the results.		
1.24	Continuance	 For the subject to continue in the study, they must meet all three of the following criteria: Visual acuity is 20/30 or better OD and OS The lens fit is acceptable OD and OS Investigator approval. 		

Visit 1: Treatment 1 Lens Fitting			
Step	Procedure	Details	
		If the Investigator does not approve the dispensing of the first study lens based on subject feedback (e.g., unsatisfactory comfort), then the study is terminated for that subject.	
1.25	Dispense	 The lenses will be dispensed for 13-15 days 1. The subjects should wear their lenses similar to the inclusion criteria: ≥ 6 hours per day, ≥ 5 days per week. 2. The lenses will be worn as daily wear only. 3. All subjects will be provided Opti-Free PureMoist to be used in a rub regime. 4. Preservative-free rewetting drops are permitted if needed. 5. A patient instruction booklet will be provided. 6. The lenses must be stored in the supplied case out of direct sunlight. Note 1: In the event a lens is lost or damaged, the subject will return to the investigator site for replacement (extra lenses cannot be given at the dispensing visit). Note 2: The subject's habitual contact lenses cannot be worn at any time during the study. Note 3: Instruct subjects to bring their spectacles to the next visit. 	

VISIT 2

The follow-up will occur 13-15 days following Visit 1. The subjects must enter the visit wearing their study contact lenses.

	Visit 2: Treatment 1 Follow-Up 1			
Step	Procedure	Details		

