## Fit Acceptance Rate

Acceptable lens fit will be assessed at all study visits (scheduled and unscheduled) for each subject eye. Fit acceptance rate will be based on the lens fit acceptance of eyes wearing the Test lens only. Fit acceptance is a binary response where Y=1 if lens fit is acceptable and Y=0 otherwise. Unacceptable is defined as unacceptable if any one of the following criteria:

- limbal exposure at primary gaze or with extreme eye movement;
- edge lift;
- excessive movement in primary up gaze;
- insufficient movement in all three of the following conditions: primary gaze, up gaze, and push up test.

Eyes with multiple unacceptable fitting events will be counted only once. Fit rates of the Control lens will also be collected but are not a primary endpoint.

The procedure is explained in the **section** in section 12 Appendix D of the study protocol. The individual lens fitting characteristics are considered as other endpoints.

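### The excessive-movement rule for an unacceptable fit differs between Visit 1 and Visit 2, so an eye that the SAP counts as a failure can be recorded as acceptable at Visit 2

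*Protocol*

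**What the plan says.** Three places define an unacceptable fit.

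- **Protocol 7.2, Visit 1, step 1.22** has two separate movement criteria. One is "excessive movement in primary and up gaze". The other is "insufficient movement in all three of the following conditions: primary gaze, up gaze, and Josephson push up".
- **Protocol 7.2, Visit 2, step 2.8** merges them into one: "insufficient or excessive movement in all three of the following conditions: primary gaze, up gaze, and Josephson push up".
- **SAP 3.1, Fit Acceptance Rate**, again has two: "excessive movement in primary up gaze" and "insufficient movement in all three of the following conditions: primary gaze, up gaze, and push up test". It applies them throughout: "Acceptable lens fit will be assessed at all study visits (scheduled and unscheduled) for each subject eye".

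Primary hypothesis 5 (Protocol 2.3.1, repeated in SAP 4.1) is that at least 90% of Test-lens eyes "will have acceptable fits across the fitting and follow-up visits". SAP 3.1 adds a counting rule: "Eyes with multiple unacceptable fitting events will be counted only once". All five primary hypotheses have to succeed for the study objective to be met.

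SAP 11.8 lists the movement and push-up grades separately, next to a yes/no item for acceptable fitting. The SAP does not say whether the primary endpoint is that yes/no item or is built from the grades.

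**The concern.** The endpoint pools the fitting and follow-up visits, yet sites are given a different excessive-movement rule at each. A site that follows step 2.8 as written can enter an acceptable fit for an eye that SAP 3.1 classes as unacceptable.

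Fit acceptance is tested on Test eyes alone against a fixed 90%. There is no Control comparison in which a lenient rule could cancel out. Subjects whose fit is unacceptable at Visit 1 are discontinued, so among dispensed subjects any new failure has to be picked up after dispensing, and the only scheduled visit for that is the one that uses the merged rule.

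The SAP does not settle the conflict. Its Introduction gives it precedence over the protocol's statistical section, not over the site procedures in Section 7.2.

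**Working it through.** **1. The criteria side by side**

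| Criterion | Step 1.22 (Visit 1) | Step 2.8 (Visit 2) | SAP 3.1 (all visits) |
|---|---|---|---|
| Limbal exposure | unacceptable | unacceptable | unacceptable |
| Edge lift | unacceptable | unacceptable | unacceptable |
| Insufficient movement | needed in all three conditions | needed in all three | needed in all three |
| Excessive movement | primary and up gaze; push-up not needed | all three, push-up included | Visit 1 structure, push-up not needed; a conjunction appears to be missing |

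Only the last row differs. Whether the missing SAP word is "and" or "or" does not matter for the conflict: an eye with excessive movement in both gazes and a normal push-up fails under either, and passes step 2.8.

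**2. Which eyes are classified differently**

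Treat each of primary gaze, up gaze and push-up as insufficient (I), acceptable (O) or excessive (E), a simplification of the grading. That gives 3 × 3 × 3 = 27 patterns. SAP 3.1 is read here with the missing "and".

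- Visit 1 and SAP rule: E-E-I, E-E-O, E-E-E and I-I-I fail, 4 of 27.
- Step 2.8, plain reading (all three insufficient, or all three excessive): I-I-I and E-E-E fail, 2 of 27. The difference is E-E-I and E-E-O. Both fail at Visit 1 and pass at Visit 2; no pattern goes the other way.
- Step 2.8, looser reading (each condition either insufficient or excessive, mixtures allowed): 2 × 2 × 2 = 8 of 27 fail. E-E-O fails only at Visit 1, and five mixed patterns fail only at Visit 2.

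The rules disagree on both readings. On the plain reading the disagreement runs one way, towards acceptance at Visit 2. These are counts of patterns, not of eyes; the documents do not say how often any pattern occurs.

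**3. The plan's own figure for this endpoint**

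Protocol Table 12 gives n = 100 and 82% power, from an exact one-sample binomial test against 0.90. The assumed true rate is not stated. The pass probability is the sum over x = 96 to 100 of C(100, x) p^x (1 − p)^(100 − x), where 96 is the smallest count with size at most 0.025 at p = 0.90 (actual size 0.0237).

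| True rate p | 0.95 | 0.96 | 0.97 | 0.98 | 0.99 |
|---|---|---|---|---|---|
| P(pass), n = 100 | 0.436 | 0.629 | 0.818 | 0.949 | 0.997 |

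The stated 82% therefore corresponds to a true rate of about 0.97. That is an inference.

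**4. Whether a size can be put on the discrepancy**

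Suppose, for illustration only, that the rules classify 2% of eyes differently.

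- n = 100, from 0.97 to 0.95: 0.818 − 0.436 = 0.382, about 38 points.
- n = 100, from 0.99 to 0.97: 0.997 − 0.818 = 0.179, about 18 points.
- 112 Test completers × 2 = 224 eyes treated as independent (211 needed), from 0.97 to 0.95: 0.992 − 0.767 = 0.225, about 22 points.

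The answer depends on the assumed discordance, the starting rate and the between-eye correlation. The documents supply none of these for this trial.

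**The case against.** The strongest reply is that this is a drafting slip with little practical weight.

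- The SAP already gives one definition for all visits, and its wording is Visit 1's with a word missing.
- Only excessive movement is affected. Subjects who fail at Visit 1 are discontinued, so an eye seen at Visit 2 has already passed the step 1.22 rule. Only excessive movement that develops later, with push-up not excessive, can change the result.
- Both steps ask for an overall subjective judgement, and the SAP refers to a procedure in a protocol appendix that is not part of the text available here. How investigators will apply step 2.8 cannot be known.
- Protocol Table 9 reports no unacceptable fits at fitting or at two weeks. If its denominator is the 860 Test eyes (430 subjects) of Table 10, which is an assumption, the one-sided 95% upper bound for any unacceptable fit is 1 − 0.05^(1/860) = 0.35% by eye, or 1 − 0.05^(1/430) = 0.7% by subject.

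Most of this stands, and it limits the size of the point. It does not remove the contradiction. The SAP's precedence does not reach the site procedures, the rule used in the historical studies is not stated, and a low expected count does not give a must-pass endpoint one definition.

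A reader might infer more than the documents support:

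- **That the chance of passing moves by 38 points.** This needs an invented 2% discordance, the steepest part of the curve, and a test on 100 independent units. The planned analysis is a Bayesian model for two correlated eyes.
- **That there are three competing rules, or that the endpoint has no definition.** There are two rules, and the SAP definition follows the first.
- **That investigators will record failing eyes as acceptable.** The text shows only that they can.

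**Conclusion.** Wrong as written, within a narrow scope. Step 2.8 conflicts with step 1.22 and with SAP 3.1 on excessive movement and on nothing else. On the plain reading of step 2.8, an eye with excessive movement in both gazes but not on push-up can be entered as acceptable at Visit 2 while meeting the SAP definition of a failure, which favours the Test lens on hypothesis 5. If mixtures count under step 2.8, the conflict remains but no longer runs in one direction.

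The effect on the primary result cannot be quantified from the documents and may be small. No sample-size figure changes. The point deserves correction because the endpoint must succeed and the remedy costs almost nothing.

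**What to change.** 1. Reconcile Protocol steps 1.22 and 2.8 and SAP 3.1 to one definition of an unacceptable fit, and correct the incomplete SAP phrase at the same time. Which clinical rule applies is for the sponsor to decide.
2. State in the SAP that the primary endpoint is the overall acceptable/unacceptable assessment made under that definition at every visit.
3. Optionally, at the fitting and two-week visits, compare that assessment with all the recorded components: limbal exposure, edge lift, primary-gaze movement, up-gaze movement and push-up. This should be a consistency check, not a replacement endpoint. Movement and push-up grades alone cannot reproduce an endpoint that also depends on limbal exposure and edge lift, and the component grades are listed only for those two visits.

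The cost is a wording change in both documents and a note to sites. The optional check uses data already planned and adds one listing.
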